Study Objectives	 The objective of the study is to assess the efficacy and safety of an oral regimen of fexinidazole, once daily for 10 days, as compared to NECT in the treatment of late-stage sleeping sickness due to T.b. gambiense. Primary Objective To demonstrate that the success rate at 18 months after the
	end of treatment is in favour of fexinidazole, or that the difference as compared to the success rate with NECT is acceptable. Secondary Objective
	 To compare the time course of the failure rate with fexinidazole and NECT from the end of treatment visit to 24 months.

1

Г

	 To compare the safety of fexinidazole with that of NECT in the treatment of late-stage sleeping sickness due to T. b. gambiense. To assess concentrations of fexinidazole and its metabolites in the plasma and cerebrospinal fluid, and the correlations
	between the concentration and the efficacy and safety of fexinidazole.
	 To compare the pharmacodynamic impact of fexinidazole and of NECT on QT/QTcF interval.
	Exploratory Objectives
	 To validate the predictive value of three logistic models for treatment success at 18 months.
	 To compare the efficacy of fexinidazole to that of melarsoprol, eflornithine and NECT using historical data as comparators.
Primary	Efficacy
Endpoint	Outcome, i.e. either success or failure, of treatment assessed at the test-of-cure visit, 18 months after the end of treatment, based on adapted WHO criteria (55).
Secondary	Efficacy
Endpoints	Outcome, i.e. either success or failure, of treatment assessed at each visit between the end of treatment and 24 months.
	Safety
	Occurrence of adverse events, including laboratory or ECG abnormalities during the observation period, i.e. from D1 to D8, and occurrence of serious adverse events between the first treatment intake and the end of the follow-up period, i.e. 18 months. Long-term safety will be assessed up to 24 months.
	Pharmacokinetics
	Pharmacokinetic analyses will be performed on all patients in the fexinidazole group using serial dry blood spots and one dry cerebrospinal fluid spot.
	Electrocardiogram (ECG)
	Categories of QT/QTcF and changes at various timepoints.
Exploratory	Surrogate Efficacy Endpoint
Endpoint	The surrogate endpoint is the actual or predicted outcome (using logistic models, if the outcome is missing) at 18 months, based on the outcome at the last visit that took place at 6 months or later

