Study Schedule	 Screening: D-15 to D-1 Baseline assessment: D-4 to D-1 Randomisation: D-1 Treatment: D1 to D10 End of Treatment Visit: D11 End of hospitalisation Visit: D13 to D18 Observation Period: D1 to D18 (for safety) Additional Follow-up Visit: 9 weeks after D1 (D64 to D70) Follow-up Visits: M3 - M6 - M12 - M18 (Test of Cure) - M24 (Additional Follow-up Visit) after D11
Statistical	Populations
Analyses	The primary analysis will be performed on the Intention-to-Treat population.
	Sensitivity analyses will be performed on patients who completed the treatment, evaluable patients and the per protocol population.
	Interim Analysis
	An interim primary analysis for success will be performed on the first 195 randomised patients who have theoretically reached the 12-month follow-up visit and will exclude patients for whom no post-treatment data are available because the patient fled the area strictly for reasons of armed conflict. The analysis will be identical to the final primary analysis with the exception of the threshold for significance, the rule for imputing missing data (see Adjustment of Type-I Error for Multiplicity) and the assessment visit, which will be 12 months instead of 18 months.

A sensitivity analysis, including all randomised patients, will be performed and will consider all patients who fled for reasons of armed conflict as failures.

If the interim primary analysis for success should not prove to be significant, no further interim secondary or sensitivity analyses will be performed. If the analysis proves to be significant, all of the interim secondary and sensitivity analyses will be performed in accordance with the approach described for the final analyses, i.e. those initially planned. In addition, the success rate at 18 months will be compared, using a superiority test, to the historical success rate for melarsoprol at 18 months, i.e. 73.7%. No adjustment of the threshold for significance will be made in this analysis. The time course of the success rate, i.e. EOT, 6 months, 12 months and 18 months, will be studied using the Kaplan-Meier approach. The cumulative failure rate at each visit will be presented graphically including historical data for melarsoprol and effornithine.

The study will be continued to completion regardless of the result of the interim analysis, and all of the analyses planned in the protocol and SAP will be performed.

Primary Analysis

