Adverse events will be graded according to the National Cancer Institute (NCI) Common Toxicity Criteria for Adverse Events (CTCAE), Version 4.03.

- Occurrence of adverse events, all grades combined, during the observation period, i.e. from D1 to D8, including:
 - any worsening of the clinical symptoms listed among the signs and symptoms to be checked prior to inclusion,
 - laboratory abnormalities \geq grade 2,
- Occurrence of any adverse events ≥ grade 3 during the observation period,
- Occurrence of any treatment-related adverse events, ≥ grade 3 and all grades combined, during the observation period,
- Occurrence of any serious adverse events between the first treatment intake and the end of the follow-up period (18 months), and between Month 18 and Month 24.

Potentially significant ECG abnormalities will be reported after centralised ECG review.

Pharmacokinetic Endpoints

PK sampling in patients in the fexinidazole group will only be performed at the first 6 investigational sites.

Concentrations of fexinidazole, M1 and M2 in whole blood and in CSF, as well as PK parameters derived from a population PK model.

- Samples of whole blood will be collected using dry blood spot (DBS) testing on a finger-prick sample at the following timepoints:
 - o on Day 8, 3 hours and 15 minutes after intake of the IP,
 - o on Day 9, 3 hours after intake of the IP,
 - $\circ~$ on Day 10, 3 hours and 7 hours and 15 minutes after intake of the IP,
 - o on Day 11, 24 hours after intake of the IP,

- o on Day 12, 48 hours after intake of the IP.
- Lumbar puncture will be performed on Day 11, 24 hours after intake of the IP for the EOT efficacy assessment. A dry CSF spot will be collected at the same time for PK analyses for all patients until the end of July 2013.

ECG Endpoints

Triplicate ECG tracings will be recorded at 2-minute intervals to assess QT interval at the following timepoints:

- At baseline for all patients
- Thereafter:
 - in patients in the fexinidazole group: on Day 4, 4 hours (H4) after intake of the IP, on Day 4 Hour 23, and on Day 10 2-3 hours after intake of the IP,
 - in patients in the NECT group: on Day 7 2-3 hours after treatment intake in the morning and on Day 10 2-3 hours after treatment intake in the morning.

Triplicate ECGs and a safety ECG will be collected for different purposes and will be analysed separately (see Section 6.3.2 ECG Recordings; p 47).

3. Study Design

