6.5. Safety Assessments, Definitions and Reporting of Adverse Events

The safety and tolerability of treatment will be assessed through routine monitoring of adverse events (AEs). During the observation period, the study personnel will collect AEs every day.

The **observation period** will extend from the start of treatment (D1) to hospital discharge, planned on D18, but potentially taking place as early as D13 if the patient's status allows it.

In addition, patients will be advised to return to the hospital/investigational centre at any time during the follow-up period if they experience any AEs, in order to undergo additional safety assessments.

Safety data will be reviewed at each meeting of the DSMB/ISC.

Safety endpoints will be classified as follows:

- Occurrence of any adverse events ≥ grade 3, including laboratory abnormalities, during the observation period. Adverse events will be graded according to the NCI CTCAE, Version 4.03 (38)
- Occurrence of any adverse events, including laboratory abnormalities, (all grades combined) during the observation period
- Occurrence of any treatment-related adverse events, including laboratory abnormalities, (≥ grade 3 and all grades combined) during the observation period
- Occurrence of any serious adverse events, including laboratory abnormalities, between the first treatment intake and the end of the followup period (18 months)
- Occurrence of any serious adverse events, including laboratory abnormalities, between the first treatment intake and the end of the additional follow-up period (24 months).

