6.5.4. AE Collection Period

The periods for collection of AEs that occur in the context of the present study are defined as follows:

- For all non-serious adverse events, the observation period extends from the first intake of the study treatment on Day 1 until hospital discharge between D12 and D18;
- For all serious adverse events, the observation period extends from enrolment of the patient in the study, i.e. after signature of the informed consent form, until the end of follow-up (24 months). SAEs will be analysed initially up to 18 months, and then up to 24

months for the additional follow-up period.

All AEs that occur during the AE collection period defined in the protocol must be recorded in the e-CRF, whether or not they are considered to be treatment related. In addition, all AEs that occur after the AE collection period, and that the Investigator considers as possibly related to the study treatment, must also be reported.

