Appendix 4 - Tables

Table 4 – Schedule of Study Procedures

Protocol-planned procedures and forms to be completed	Pre-screening and Screening	Baseline	e Treatment period										End-of-Treatment Visit until End-of- Hospitalisation Visit			Follow-up period (months)
Timepoint	D-15 to D-1	D-4 to D- 1	D1	D2	D3	D4	D5	D6	D7	D8	D9	D10	D11	D12	D13-D18	Week 9 ³ 3 – 6 – 12 – 18 -24 months
Detection of parasite in blood and/or lymph	Х												х			х
Lumbar puncture (parasite and white blood cells in CSF)	x												х			x ¹
Informed consent (before any additional medicines or study-specific procedures)	×	Check														
Pretreatment of helminthiasis (+ 3-day recovery period)	x															
Rapid diagnostic test and/or thick blood smear for malaria	Х															
Pretreatment of malaria if necessary (+ 3-day recovery period)	x															
Karnofsky score	Х	Check														х
Safety ECG	Х	Check														
Safety ECG (fexinidazole group only)				х	х	х										
Urine pregnancy test		х													х	x (only at 3 months)
Inclusion and exclusion criteria	Х	х														
Randomisation		х														
Demographic data	Х															
Medical history	Х															х
Signs and symptoms of HAT		х													х	х
Vital signs	Х	х					х			х			х		х	х
Physical examination		х					х			х			х		х	х
Neurological examination		х					х			х			х		х	х
Haematology and biochemistry	Х	х					х			х			х			x (only at Week 9)
Haematocrit ²	Х															
Urine analysis	Х	х											х			

¹ Except for 3-month follow-up visit unless the patient presents with clinical symptoms or signs of HAT.

² Only for patients at sites where PK sampling is performed.

³ Only at Week 9 after D1, perform sampling for haematology and biochemistry, physical examination and neurological examination.

Protocol-planned procedures and forms to be completed	Pre- screening and Screening	Baseline		Treatment period						End-of-Treatment Visit until End-of-Hospitalisation Visit			Follow-up period (months)			
Timepoint	D-15 to D-1	D-4 to D-1	D1	D2	D3	D4	D5	D6	D7	D8	D9	D10	D11 (EOT)	D12	D13-D18	Week 9 3 – 6 – 12 – 18 -24 months
Triplicate ECGs –fexinidazole group		x				x D4H4 D4H23						x D10H2-H3				
Triplicate ECGs – NECT group		x							x D7H2- H3			x D10H2-H3				
Administration of fexinidazole			х	х	х	х	х	х	х	х	х	х				
Administration of NECT			х	х	х	х	х	х	х	х	х	х				
Treatment-related adverse events			х	х	х	х	х	х	х	х	х	х	х	х	х	

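### The Summary and section 2.2.2 gloss the safety observation period as D1 to D8, against the D1-to-discharge (D13 to D18) period defined in section 6.5

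*Protocol*

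**What the plan says.** Two places give the short window. Section 2.2.2 (Safety Endpoints) counts adverse events of all grades "during the observation period, i.e. from D1 to D8, including" worsening of baseline symptoms and laboratory abnormalities of grade 2 or higher. The next two bullets there, on events of grade 3 or higher and on treatment-related events, use the same term and so take the same days. The Protocol Summary (Secondary Endpoints, Safety) counts adverse events "including laboratory or ECG abnormalities during the observation period, i.e. from D1 to D8".

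The other statements are longer. The Summary's Study Schedule has "Observation Period: D1 to D18 (for safety"). Section 6.5 defines the observation period formally: it "will extend from the start of treatment (D1) to hospital discharge, planned on D18, but potentially taking place as early as D13". Section 6.5.1 puts its last day between D13 and D18, and section 6.5.3 has D1 to D18 or earlier discharge. Section 6.5.4 collects non-serious events until discharge, which it places between D12 and D18.

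On what is recorded, section 6.5.4 says that all events in the collection period "must be recorded in the e-CRF, whether or not they are considered to be treatment related", and sections 6.5.1 and 6.5.5 agree. Table 4, however, labels its two event rows "Treatment-related adverse events" and, likewise, treatment-related serious adverse events.

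**The concern.** The endpoint section fixes what is counted. Section 9.9 (Safety Analyses) gives no window of its own that would override it. A programmer who takes the endpoint from section 2.2.2 or from the Summary would therefore stop counting non-serious events at D8, although safety compared with NECT is a stated secondary objective (section 2.1.3).

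On the protocol's own account the omitted days are informative. Section 1.7 reports a marked, reversible liver-enzyme rise in one volunteer just after 14 days at the highest dose, and relates liver-test abnormalities to dose and overall exposure. Section 1.9 gives avoidance of exposure-related enzyme rises as a reason for limiting treatment to 10 days. Section 1.8 gives M2 a mean half-life of about 24 hours, so exposure continues after the last dose. The D11 laboratory visit is the in-hospital visit placed to see such an effect.

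The cut also falls unevenly on the regimens. D1 to D8 contains all 7 eflornithine days, but only 8 of the 10 fexinidazole days and 8 of the 10 nifurtimox days. The documents do not show which way this would move the comparison.

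**Working it through.** No power or error-rate figure is involved. The check is day arithmetic and a comparison of the texts.

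**Inputs**
- Dosing: D1 to D10 in both arms (section 6.1).
- Hospital stay after treatment: 3 to 8 days (section 7).
- In-hospital post-baseline haematology and biochemistry: D5, D8, D11 (section 6.3.3).
- Post-baseline urine analysis in Table 4: D11 only.
- Last triplicate ECG: D10 in both arms (section 6.3.2).
- Possible make-up day for a missed dose: one (section 8.1).

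**Which end day fits the protocol's own durations**
- Earliest discharge: D10 + 3 = D13.
- Latest discharge: D10 + 8 = D18.
- These match section 6.5 and Table 3. D8 matches neither and falls before the end of dosing. D12, in section 6.5.4, is one day earlier than the D13 used elsewhere.

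**What lies after D8**
- Dosing days: 10 − 8 = 2 (D9 and D10), or 11 − 8 = 3 calendar days up to the last dose if a make-up day moves it to D11.
- Observation days: 13 − 8 = 5 with discharge on D13, and 18 − 8 = 10 with discharge on D18. As a share of the period, this is 5/13 = 38% to 10/18 = 56%.
- Laboratory days: one of the three in-hospital blood draws (D11), and the only post-baseline urine analysis in Table 4.
- ECG: an abnormality at or after the D10 recording, where it is counted as an adverse event under the Summary wording.

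**What is not touched by the D8 limit**
- QT/QTcF: section 2.2.2 lists separate ECG endpoints that name Day 10 in both arms, and section 9.10 analyses them under their own plan.
- Laboratory values: the changes over time, shift tables and listings in section 9.9 carry no D8 limit.
- Serious adverse events: section 2.2.2 gives them their own window, to 18 months and then to 24 months.
- Events leading to discontinuation: section 9.9 tabulates them with no D8 limit.
- Data capture: sections 6.5.3 to 6.5.5 require recording to discharge.

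**Result.** The affected set is non-serious adverse events with onset after D8, including laboratory or ECG abnormalities counted as such.

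**The case against.** The strongest reply is that this is a slip and not a choice of window. The endpoint term is the observation period, and the D8 is only an explanatory aside in two sentences. Section 6.5 defines the term formally and then restates the same safety endpoints against it without mentioning D8. Table 4 marks event recording through D13 to D18. A typing error for D18 is plausible, and so is confusion with D8 counted from the end of treatment, which Table 3 equates with D18. The documents do not say which, so the origin remains an inference. This reply stands as to intent: nothing suggests a deliberate cut-off. It does not remove the need for a correction, because the aside appears twice, in the places from which an endpoint is normally taken.

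Three stronger readings are tempting, and the documents support none of them. A reader might infer that the D10 triplicate ECGs or the D11 laboratory results drop out of the analysis. They do not, given the separate ECG endpoints and the unrestricted laboratory summaries. A reader might take the loss as a flat 10 of 18 days. That is the upper end, since discharge is allowed from D13. A reader might also infer from the Table 4 labels that open-label investigators will record only events they judge related to treatment. The labels do contradict sections 6.5.1, 6.5.4 and 6.5.5, but those three explicit instructions govern recording, and nothing in the documents shows that sites would follow the row label instead.

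**Conclusion.** The contradiction is real and lies in the endpoint definition, not in data collection. Read literally, the Summary and section 2.2.2 remove from the secondary safety comparison the non-serious adverse events with onset on dosing days D9 and D10 and over the rest of the stay, 5 to 10 observation days in all. They also remove abnormalities on the D11 blood and urine tests counted as adverse events. How many events that is cannot be stated, because the protocol gives no expected event rates by day.

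The conclusion assumes that an analyst would apply the endpoint text as written. If the section 6.5 definition is applied, nothing is lost and the defect is one of wording. The protocol does not say which text takes precedence, so it should be settled in the text. The Table 4 labels are a secondary inconsistency.

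**What to change.** In the Protocol Summary (Secondary Endpoints, Safety) and in section 2.2.2, replace the D1 to D8 gloss with the section 6.5 observation period: start of treatment to hospital discharge, D18 at the latest. A cross-reference to section 6.5 would keep the two from drifting apart again. Reconcile the D12 in section 6.5.4 with the D13 in sections 6.1, 6.5 and 6.5.1 and in Table 3, so that one range of discharge days appears throughout. As a secondary correction, relabel the two Table 4 rows as all adverse events and all serious adverse events, to match sections 6.5.4 and 6.5.5.

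The cost is wording edits in four places: the Summary, section 2.2.2, section 6.5.4 and Table 4. Correcting the endpoint window and the row labels needs no new visit, sample or data item, because events are already to be recorded to discharge.

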4.1. Enrolment/Inclusion Procedures

The study will be conducted in at least 6 centres in the DRC and the Central African Republic (CAR).

Patients will be recruited in one of three ways:

- a. Patients may present spontaneously at the investigational centre and will undergo routine assessment at the centre, including testing for *T.b. gambiense* in the blood, lymph and CSF.
- b. Patients may be referred to the investigational centre after being diagnosed with late-stage HAT by one of the mobile teams in the field (see Section 1.4 Routine Case Detection and Management; p 18). In that case, patients will not undergo a second lumbar puncture. They will receive a staging certificate from the mobile team and may participate in the study,

if they so desire, without undergoing a second lumbar puncture. For ethical reasons, the lumbar puncture planned at inclusion will not be performed in these patients. However, if the staging of HAT is questionable, i.e. negative findings on CSF testing for parasite and CSF WBC between 19 and $22/\mu$ L inclusive, the patient will be asked to undergo a second lumbar puncture to confirm the stage. If the patient refuses, s/he will not be included in the study and will be treated in accordance with usual practice in the centre.

- c. Patients may be referred to the investigational centre by a less wellequipped mobile team that was not able to determine the stage of HAT and will then undergo assessment as described in point (a) above.
- d. A new microscope has been provided on each site (February 2015). This microscope allows picture or video capture (maximum 5 sec. of video) of the trypanosomes on the slide as well as the cells counting in the sampling (blood, node, LCR). The photographic and video recordings are identified per patients, date and time of recording. Before stored in a specific database, all the recording will be anonymized as the other data in order to maintain the confidentiality. They will be saved and kept on site as well as on a specific data base (powerfolder). This procedure will be performed for the follow-up visits too.

During the screening process prior to inclusion and before the informed consent form is signed, patients will be considered as "pre-screened patients". Patients who fulfil the pre-inclusion criteria, i.e. not requiring any study-specific procedures, will be invited to participate in the study and will receive the necessary information before they give their informed consent.

For patients to be enrolled in the study, they must sign an informed consent form after the Investigator or a delegate has provided explanations and prior to any study-specific procedures. Patients will then be considered as "screened patients".

As previously mentioned, the initial study-specific procedures do not include lumbar puncture unless it is required in order to confirm the staging of HAT, when the staging based on CSF examination by the mobile team in the village is questionable.

The Investigator or a delegate must record the date of the screening visit, the patient's initials, the patient's number, referral source, status at the time of the screening visit, date of collection of informed consent, date of enrolment/ inclusion and the date of randomisation, as well as the treatment number or reason for non-enrolment, if appropriate.

The enrolment/inclusion procedures must be carried out between 1 and 15 days before the planned start of the study treatment. The procedures are described in Section 6 Schedule of Assessments (p 44). The procedures include a complete

history-taking, a physical examination, testing and treatment for malaria, treatment for helminthiasis, haematological and biochemical assessments, ECG and urine pregnancy test.

